STUDY PROTOCOL

Effect of Vaxoral[®] (OM-85) on frequency of upper respiratory tract infections and size of adenoid tissue in preschool children with adenoid hypertrophy

Study Product(s)	Vaxoral [®] (OM-85)			
Indication	Recurrent RTIs, adenoid hypertrophy			
Sponsor	[name] Maternity and Children Research and Training			
	Hospital, Department of Pediatric Allergy and Immunology,			
	Ankara, TURKEY			
Anticipated	Taulasa			
Countries	Turkey			
Introduction	OM-85 significantly reduces RTIs in children. This effect was			
	proved by many clinical studies and meta-analyses ¹ . A Cochrane			
	meta-analysis first published in 2006 and updated recently (Del-			
	Rio-Navarro 2012) showed that immunostimulants (IS) could			
	reduce acute RTIs (ARTIs) by almost 39% when compared to			
	placebo. Among the different IS, OM-85 showed the most robust			
	evidence with 4 trials of "A quality" according to the Cochrane			
	grading criteria. Pooling six OM-85 studies, the Cochrane review			
	reported a mean number of ARTIs reduction by -1.20 [95% CI: -			
	1.75, -0.66] and a percentage difference in ARTIs by -35.9% [95%			
	CI: -49.46 , -22.35] compared to placebo ¹ .			
	Adenoid hypertrophy (AH) is one of the most important respiratory			
	disease in preschool children ² . In normal conditions adenoid tissue			
	enlarges up to 5 years and become smaller afterwards. But in some			
	children who have recurrent URTIs, it keeps growing and this can			
	be associated with complications ² . AH may cause recurrent			
	respiratory infections and each infection contributes to enlargement			
	of adenoid tissue thus promoting a vicious cycle. Additionally			
	enlarged adenoids are known to be reservoir for microbes and cause			
	of recurrent or long lasting RTIs ³ .			
	AH is associated with chronic cough, recurrent and chronic			

sinusitis, recurrent tonsillitis, recurrent otitis media with effusion, recurrent other respiratory problems such as, nasal obstruction and sleep disturbances, sleep apneas²⁻³. Eventually, AH causes loss of appetite and growth delay; it is often associated with misuse or over use of antibiotics and often eventually requires surgery. It decreases quality of life both in children and parents and it represents a burden not only for families but also for HCS and society due to increased health cost⁴.

In one study which investigated the structural and immunological aspects of tonsils and adenoids of 105 children (54 males and 51 females, aged between 4 and 18 years) who were affected by chronic inflammatory hypertrophy of palatine tonsils and adenoids which had not responded to previous medical treatments and who underwent adenotonsillectomy because of recurrent inflammatory episodes with fever, it was demonstrated that deficit in the activation of the immune system could be represented by the small quantity of mRNAs for interleukin-2 (IL-2) and interleukin-4 (IL-4) detected in our population, suggesting a defective activation of Th1 and Th2 lymphocytes⁵.

Clinical research question: Can OM-85 reduce the recurrence of infections in children with AH by stimulating the immunological response of the host and therefore, as a consequence reduce the size of adenoid tissue in children with adenoid hypertrophy?

Can this prevent further complications as surgery need?

References:

- Del-Rio-Navarro BE et al. Immunostimulants for preventing respiratory tract infection in children (Review) Evid.-Based Child Health (A Cochrane Review Journal).2012;7(2): 629–717.
- Zautner AE. Adenotonsillar disease. Recent Pat Inflamm Alergy Drug Discov. 2012 May;6 (2):121-9.

	4. Ericsson E, Lundeborg I, Hultcrantz E. Child behavior and			
	quality of life before and after tonsillotomy versus tonsillectomy.			
	Int J Pediatr Otorhinolaryngol. 2009 Sep;73 (9):1254-62.			
	5. Passali D, et al. Structural and immunological characteristics of			
	chronically inflamed adenotonsillar tissue in childhood. Clinical			
	and Diagnostic Laboratory Immunology 2004; 11 (6): 1154-			
	1157			
	OM-85 is an oral bacterial lysate of 21 different strains of 8 species			
Rationale	and sub-species of the most common respiratory tract pathogens			
	that has been administered in millions of children above 1 year of			
	age. OM-85 stimulates the innate immune system by improving			
	alveolar macrophage activity in the BAL fluid of patients with			
	airway disease, increasing dendritic cells activation and increasing			
	antibodies in the lung of patients with airway diseases. OM-85			
	stimulates Th1 immunity and inhibits Th2 immunity ¹ .			
	Its clinical efficacy in reducing the rate of RRTIs in children is			
	supported by several well-designed and conducted clinical studies			
	and it has showed a good benefit risk profile, unchanged in nature			
	and frequency over more than 30 years of clinical paediatric use.			
	A recent meta-analysis by Schaad et al. 2010 ² of 8 double-blind			
	placebo-controlled trials conducted in children aged 1-12 years			
	affected by recurrent infective episodes (\geq 3 RTIs in 6 months) has			
	shown that the administration of OM-85 significantly reduced the			
	mean number of RTIs by 35% vs placebo and that a lower			
	proportion of treated patients (26.2%) experienced RRTIs. This			
	effect was more evident in patients with the highest number of			
	infectious in the year prior to study $entry^2$.			
	The majority of studies used a children posology of 1 daily dose			
	(3.5mg) for 10 days repeated for 3 consecutive months followed by			
	3 months or 9 months follow-up. In one study 2 cycles (10 days/3			
	months) at a 6-months intervals were used.			
	An effective and well tolerated prevention of RRTIs with OM-85			
	could result not only in a positive effect on children's quality of life			
	courd result not only in a positive cricer on children's quanty of file			

	but also in economic benefit for patients' families and societies as		
	recently reported in a pharmacoeconomic study by Zaniolo et al.		
	2013^3 and Ravasio et al. 2015^4 .		
	Because OM-85 significantly reduces RTIs in children, it is		
	expected to be able to reduce the adenoid tissue size as a		
	consequence of fewer inflammatory RTIs.		
	References:		
	1. De Benedetto F, at al. Prevention of respiratory tract infections		
	with bacterial lysate OM-85 Broncho-munal in children and		
	adults: a state of the art. Multidiscip Respir Med. 2013 May		
	22;8(1):33		
	2. Schaad UB. OM-85 BV, an immunostimulant in pediatric		
	recurrent respiratory tract infections: a systematic review.		
	World J Pediatr 2010; 6(1): 5-12.		
	3. Zaniolo O et al. Costo/efficacia della prevenzione di infezioni		
	alle prime vie aeree mediante un estratto batterico		
	immunostimolante aspecifico (OM-85). Farmaeconomia e		
	percorsi terapeutici 2013; 3(6):169-184		
	4. Ravasio R. Economic analysis of the immunostimulant OM-85		
	for the prevention of paediatric recurrent upper respiratory tract		
	infections. Global & Regional Health Technology Assessment		
	2015; 0(0): 00-00. DOI: 10.5301/GRHTA.5000200.		
Objectives			
J	Primary Objective:		
	• Reduction of number of RTIs within 12 months		
	Secondary Objective(s):		
	Reduction in duration of RTIs		
	Reduction of antibiotic use		
	• Reduction of absenteeism (missed school days or missed days of		
	work for parents)		
	Adenoid and tonsil health survey		

 Reduction of the size of adenoid tissue (described in appendix 3) Reduction of surgery need Design, incl. This is a randomised, double-blind, placebo-controlled, parallel group, phase IV study. First group will receive OM-85 (10-10-10 standard treatment regimen) Second group will receive matching placebo at the same posology (10-10-10). A second cure of treatment will be given 6 months after inclusion. Patients will be recruited from 01 September 2017 to 01 March 2018. The trial will begin in September 2017 and will be completed in March 2019. By this way every patient will be studied over all seasons (1 year study). Children (age: 2-6 years) Who experienced recurrent RTIs (at least 3 episodes in 6 months before the inclusion) Who have symptoms of AH (snoring; mouth breathing awake; mouth breathing asleep; nasal congestion; hyponasal voice; chronic nasal discharge; daytime drowsiness, or hyperactivity; restless sleep; sleep apnoca <15 sec; night cough; and poor oral intak/weight loss) based on the symptoms score questionnaire (described in appendix 1). Exclusion Criteria A Atopy Gastroesophageal reflux Immune deficiency Asthma or allergic rhinitis 		-					
• Reduction of surgery needDesign, incl.This is a randomised, double-blind, placebo-controlled, parallel group, phase IV study. First group will receive OM-85 (10-10-10 standard treatment regimen) Second group will receive matching placebo at the same posology (10-10-10). A second cure of treatment will be given 6 months after inclusion. Patients will be recruited from 01 September 2017 to 01 March 2018. The trial will begin in September 2017 and will be completed in March 2019. By this way every patient will be studied over all seasons (1 year study).Inclusion Criteria• Children (age: 2-6 years) • Who experienced recurrent RTIs (at least 3 episodes in 6 months before the inclusion) • Who have symptoms of AH (snoring; mouth breathing awake; mouth breathing asleep; nasal congestion; hyponasal voice; chronic nasal discharge; daytime drowsiness, or hyperactivity; restless sleep; sleep apnoca <15 sec; night cough; and poor oral intak/weight loss) based on the symptoms score questionnaire (described in appendix 1).Exclusion Criteria• Atopy Gastroesophageal reflux • Immune deficiency • Asthma or allergic rhinitis		(described in appendix 1)					
Design, incl. This is a randomised, double-blind, placebo-controlled, parallel group, phase IV study. First group will receive OM-85 (10-10-10 standard treatment regimen) Second group will receive matching placebo at the same posology (10-10-10). A second cure of treatment will be given 6 months after inclusion. Patients will be recruited from 01 September 2017 to 01 March 2018. The trial will begin in September 2017 and will be completed in March 2019. By this way every patient will be studied over all seasons (1 year study). Children (age: 2-6 years) Who experienced recurrent RTIs (at least 3 episodes in 6 months before the inclusion) Who have symptoms of AH (snoring; mouth breathing awake; mouth breathing asleep; nasal congestion; hyponasal voice; chronic nasal discharge; daytime drowsiness, or hyperactivity; restless sleep; sleep apnoea <15 sec; night cough; and poor oral intak/weight loss) based on the symptoms score questionnaire (described in appendix 1). Exclusion Criteria Atopy Gastroesophageal reflux Immune deficiency Asthma or allergic rhinitis 		Reduction of the size of adenoid tissue (described in appendix 3)					
Treatmentgroup, phase IV study.First group will receive OM-85 (10-10-10 standard treatment regimen)Second group will receive matching placebo at the same posology (10-10-10).A second cure of treatment will be given 6 months after inclusion. Patients will be recruited from 01 September 2017 to 01 March 2018. The trial will begin in September 2017 and will be completed in March 2019. By this way every patient will be studied over all seasons (1 year study).Inclusion Criteria• Children (age: 2-6 years)• Who experienced recurrent RTIs (at least 3 episodes in 6 months before the inclusion)• Who have symptoms of AH (snoring; mouth breathing awake; mouth breathing asleep; nasal congestion; hyponasal voice; chronic nasal discharge; daytime drowsiness, or hyperactivity; restless sleep; sleep apnoea <15 sec; night cough; and poor oral intake/weight loss) based on the symptoms score questionnaire (described in appendix 1).Exclusion Criteria• Atopyfication contine (Gastroesophageal reflux (Martine)• Atopy• Asthma or allergic rhinitis		Reduction of surgery need					
First group will receive OM-85 (10-10-10 standard treatment regimen)Second group will receive matching placebo at the same posology (10-10-10).A second cure of treatment will be given 6 months after inclusion. Patients will be recruited from 01 September 2017 to 01 March 2018. The trial will begin in September 2017 and will be completed in March 2019. By this way every patient will be studied over all seasons (1 year study).Inclusion Criteria• Children (age: 2-6 years) • Who experienced recurrent RTIs (at least 3 episodes in 6 months before the inclusion) • Who have symptoms of AH (snoring; mouth breathing awake; mouth breathing asleep; nasal congestion; hyponasal voice; chronic nasal discharge; daytime drowsiness, or hyperactivity; restless sleep; sleep apnoea <15 sec; night cough; and poor oral intake/weight loss) based on the symptoms score questionnaire (described in appendix 1).Exclusion Criteria• Atopy • Gastroesophageal reflux • Immune deficiency • Asthma or allergic rhinitis	Design, incl.	This is a randomised, double-blind, placebo-controlled, parallel					
regimen)Second group will receive matching placebo at the same posology (10-10-10).A second cure of treatment will be given 6 months after inclusion. Patients will be recruited from 01 September 2017 to 01 March 2018. The trial will begin in September 2017 and will be completed in March 2019. By this way every patient will be studied over all seasons (1 year study).Inclusion Criteria• Children (age: 2-6 years) • Who experienced recurrent RTIs (at least 3 episodes in 6 months before the inclusion) • Who have symptoms of AH (snoring; mouth breathing awake; mouth breathing asleep; nasal congestion; hyponasal voice; chronic nasal discharge; daytime drowsiness, or hyperactivity; restless sleep; sleep apnoea <15 sec; night cough; and poor oral intake/weight loss) based on the symptoms score questionnaire (described in appendix 1).Exclusion Criteria• Atopy • Atopy • Asthma or allergic rhinitis	Treatment	group, phase IV study.					
Second group will receive matching placebo at the same posology (10-10-10). A second cure of treatment will be given 6 months after inclusion. Patients will be recruited from 01 September 2017 to 01 March 2018. The trial will begin in September 2017 and will be completed in March 2019. By this way every patient will be studied over all seasons (1 year study).Inclusion Criteria• Children (age: 2-6 years) • Who experienced recurrent RTIs (at least 3 episodes in 6 months before the inclusion) • Who have symptoms of AH (snoring; mouth breathing awake; mouth breathing asleep; nasal congestion; hyponasal voice; chronic nasal discharge; daytime drowsiness, or hyperactivity; restless sleep; sleep apnoea <15 sec; night cough; and poor oral intake/weight loss) based on the symptoms score questionnaire (described in appendix 1).Exclusion Criteria• Atopy • Gastroesophageal reflux • Immune deficiency • Asthma or allergic rhinitis		First group will receive OM-85 (10-10-10 standard treatment					
(10-10-10).A second cure of treatment will be given 6 months after inclusion.Patients will be recruited from 01 September 2017 to 01 March2018. The trial will begin in September 2017 and will be completedin March 2019.By this way every patient will be studied over all seasons (1 yearstudy).Inclusion Criteria• Children (age: 2-6 years)• Who experienced recurrent RTIs (at least 3 episodes in 6 months before the inclusion)• Who have symptoms of AH (snoring; mouth breathing awake; mouth breathing asleep; nasal congestion; hyponasal voice; chronic nasal discharge; daytime drowsiness, or hyperactivity; restless sleep; sleep apnoea <15 sec; night cough; and poor oral intake/weight loss) based on the symptoms score questionnaire (described in appendix 1).Exclusion Criteria• Atopy• Gastroesophageal reflux • Immune deficiency • Asthma or allergic rhinitis		regimen)					
A second cure of treatment will be given 6 months after inclusion. Patients will be recruited from 01 September 2017 to 01 March 2018. The trial will begin in September 2017 and will be completed in March 2019. By this way every patient will be studied over all seasons (1 year study).Inclusion Criteria• Children (age: 2-6 years) • Who experienced recurrent RTIs (at least 3 episodes in 6 months before the inclusion) • Who have symptoms of AH (snoring; mouth breathing awake; mouth breathing alseep; nasal congestion; hyponasal voice; chronic nasal discharge; daytime drowsiness, or hyperactivity; restless sleep; sleep apnoea <15 sec; night cough; and poor oral intake/weight loss) based on the symptoms score questionnaire (described in appendix 1).Exclusion Criteria• Atopy • Gastroesophageal reflux • Immune deficiency • Asthma or allergic rhinitis		Second group will receive matching placebo at the same posology					
Patients will be recruited from 01 September 2017 to 01 March 2018. The trial will begin in September 2017 and will be completed in March 2019. By this way every patient will be studied over all seasons (1 year study).Inclusion Criteria• Children (age: 2-6 years) • Who experienced recurrent RTIs (at least 3 episodes in 6 months before the inclusion) • Who have symptoms of AH (snoring; mouth breathing awake; mouth breathing asleep; nasal congestion; hyponasal voice; chronic nasal discharge; daytime drowsiness, or hyperactivity; restless sleep; sleep apnoea <15 sec; night cough; and poor oral intake/weight loss) based on the symptoms score questionnaire (described in appendix 1).Exclusion Criteria• Atopy • Asthma or allergic rhinitis		(10-10-10).					
2018. The trial will begin in September 2017 and will be completed in March 2019. By this way every patient will be studied over all seasons (1 year study).Inclusion Criteria• Children (age: 2-6 years) • Who experienced recurrent RTIs (at least 3 episodes in 6 months before the inclusion) • Who have symptoms of AH (snoring; mouth breathing awake; mouth breathing asleep; nasal congestion; hyponasal voice; chronic nasal discharge; daytime drowsiness, or hyperactivity; restless sleep; sleep apnoea <15 sec; night cough; and poor oral intake/weight loss) based on the symptoms score questionnaire (described in appendix 1).Exclusion Criteria• Atopy • Gastroesophageal reflux • Immune deficiency • Asthma or allergic rhinitis		A second cure of treatment will be given 6 months after inclusion.					
in March 2019.By this way every patient will be studied over all seasons (1 year study).Inclusion Criteria• Children (age: 2-6 years) • Who experienced recurrent RTIs (at least 3 episodes in 6 months before the inclusion) • Who have symptoms of AH (snoring; mouth breathing awake; mouth breathing asleep; nasal congestion; hyponasal voice; chronic nasal discharge; daytime drowsiness, or hyperactivity; restless sleep; sleep apnoea <15 sec; night cough; and poor oral intake/weight loss) based on the symptoms score questionnaire (described in appendix 1).Exclusion Criteria• Atopy • Gastroesophageal reflux • Immune deficiency • Asthma or allergic rhinitis		Patients will be recruited from 01 September 2017 to 01 March					
By this way every patient will be studied over all seasons (1 year study).Inclusion Criteria• Children (age: 2-6 years)• Who experienced recurrent RTIs (at least 3 episodes in 6 months before the inclusion)• Who have symptoms of AH (snoring; mouth breathing awake; mouth breathing asleep; nasal congestion; hyponasal voice; chronic nasal discharge; daytime drowsiness, or hyperactivity; restless sleep; sleep apnoea <15 sec; night cough; and poor oral intake/weight loss) based on the symptoms score questionnaire (described in appendix 1).Exclusion Criteria• Atopy• Atopy • Gastroesophageal reflux • Immune deficiency • Asthma or allergic rhinitis		2018. The trial will begin in September 2017 and will be completed					
study). Inclusion Criteria • Children (age: 2-6 years) • Who experienced recurrent RTIs (at least 3 episodes in 6 months before the inclusion) • Who have symptoms of AH (snoring; mouth breathing awake; mouth breathing asleep; nasal congestion; hyponasal voice; chronic nasal discharge; daytime drowsiness, or hyperactivity; restless sleep; sleep apnoea <15 sec; night cough; and poor oral intake/weight loss) based on the symptoms score questionnaire (described in appendix 1). Exclusion Criteria • Atopy • Atopy • Atopy • Atomy • Atomy • Asthma or allergic rhinitis • Asthma or allergic rhinitis		in March 2019.					
Inclusion Criteria • Children (age: 2-6 years) • Who experienced recurrent RTIs (at least 3 episodes in 6 months before the inclusion) • Who have symptoms of AH (snoring; mouth breathing awake; mouth breathing asleep; nasal congestion; hyponasal voice; chronic nasal discharge; daytime drowsiness, or hyperactivity; restless sleep; sleep apnoea <15 sec; night cough; and poor oral intake/weight loss) based on the symptoms score questionnaire (described in appendix 1). Exclusion Criteria • Atopy • Atopy • Asthma or allergic rhinitis		By this way every patient will be studied over all seasons (1 year					
Inclusion Criteria • Who experienced recurrent RTIs (at least 3 episodes in 6 months before the inclusion) • Who have symptoms of AH (snoring; mouth breathing awake; mouth breathing asleep; nasal congestion; hyponasal voice; chronic nasal discharge; daytime drowsiness, or hyperactivity; restless sleep; sleep apnoea <15 sec; night cough; and poor oral intake/weight loss) based on the symptoms score questionnaire (described in appendix 1). Exclusion Criteria • Atopy • Atopy • Atomy • Immune deficiency • Asthma or allergic rhinitis		study).					

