	gamma globulins, or anticonvulsive drugs within the				
	previous 6 months.				
Endpoints	Primary Endpoint: Cumulative number of RTIs over the 12				
	months.				
	monuis.				
	Secondary Endpoints:				
	• Duration in days of RTIs				
	• Antibiotic use (n. of cycles and days)				
	Missed school/work days				
	• Adenoid and tonsil survey (described in appendix 1 of the				
	original protocol)				
	• Size of adenoid tissue over the 12 months according to				
	radiographic and flexible nasopharyngoscopic evaluation (described				
	in appendix 3 of original protocol).				
	Surgery need				
	• AEs				
	Patients will be recruited from 01 September 2017 to 01 March				
Procedures	2018. The trial will begin in 01 September 2017 and will be				
	completed 01 March 2019.				
	Children with the ages of 2-6 years who have recurrent RTIs and				
	AH will be evaluated for the eligibility for the study. When eligible				
	for the study, children's all demographic characteristics will be				
	recorded (Table 1). Eligible children will be evaluated by ear-nose-				
	throat (ENT) specialist and flexible laryngoscopy and radiographic				
	evaluation of adenoid size will be performed in order to measure the				
	adenoid size. All children will be evaluated by an allergy specialist.				
	Complete blood count, serum IgG, IgA, IgE, IgM will be measured.				

Skin prick test will be performed with common allergens.

All children will be randomized into two study arms (active treatment and placebo). OM-85 3.5 mg capsule or placebo will be given according to the standard treatment schedule (10-10-10) for the three consecutive months. All patients will receive 2 cures of treatment at the beginning and 6 Months after inclusion in the study. Every patients will be followed-up for 12 months.

Patients (and care giver/parents) will be given a symptom score form (Table 2) in order to record all nasal symptoms, signs and duration of RTIs, antibiotic use, days of absenteeism from school and from work for family members, monthly.

All patients will be asked to come to the clinic when they have symptoms of RTI in order to diagnose the type of RTIs. Then they will be asked to complete the infection form during the acute RTIs (Table 3).

Every 3 months they will fill in the Tonsil and Adenoid Health Status Survey (Table 4).

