Statistical method:

All analyses will be performed with a commercially available software program (SPSS Statistical Software, version 11.5; SPSS, Inc, Chicago, Ill). The Shapiro-Wilks test will be used to evaluate normality of the distributions collected. When variables were normally distributed, they were expressed as means (SDs); otherwise, they will be expressed as medians and interquartile ranges (25th-75th percentiles). The χ^2 test will be used for categorical variables and expressed as observation counts (in percentages). An ANOVA (or Mann-Whitney U depending on the normality of data) statistics will be used to compare means between both treatment groups for continuous variables. Bonferroni multiple comparison test will be used to compare paired intervals (0-3, 0-6 months). All P values are 2-tailed; a P value of less than .05 are considered statistically significant.

Sample Size:

In one study OM-85 group showed 3 less RTIs compared with placebo over 12 months period. A sample size of 54 randomized patients (27 per group) will provide at least 80% power to detect a mean difference of at least 2.0 RTIs between the two groups assuming a SD of 2.55 and assuming a drop-rate of 20% after 6 months, total of 68 patients (34 per group) will be recruited to the study.¹

Reference:

María Dolores Gutiérrez-Tarango and Arturo Berber. Safety and Efficacy of Two Courses of OM-85 BV in the Prevention of Respiratory Tract Infections in Children During 12 Months. CHEST 2001; 119:1742–1748

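### The 12-month adenoid-size comparison ignores age and baseline size, although ages 2-6 span the protocol's own growth turning point: a loss of precision, not a bias between arms

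*Protocol*

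**What the plan says.** On the natural course, the protocol's Introduction says that in normal conditions adenoid tissue "enlarges up to 5 years and become smaller afterwards". The next sentence qualifies this: in some "children who have recurrent URTIs, it keeps growing and this can" bring complications.

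On who is studied and for how long, the first inclusion criterion begins "Children (age: 2-6 years". Entry also requires at least 3 RTIs in the preceding 6 months and symptoms of adenoid hypertrophy. Procedures adds: "Every patients will be followed-up for 12 months".

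On the outcome, the secondary endpoints include "Size of adenoid tissue over the 12 months according to" radiography and flexible nasopharyngoscopy. Appendix 3 defines the two measures: the AC/SP ratio and the perceived percent obstruction of the choana. Adenoid size is also in the trial's title.

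On design and analysis, the protocol states: "This is a randomised, double-blind, placebo-controlled, parallel group, phase IV study". Procedures says "All children will be randomized into two study arms"; no stratification by age is mentioned. The SAP (Statistical method), like the protocol's Statistical Methods, says: "An ANOVA (or Mann-Whitney U depending on the normality of data) statistics will be used to compare means between both treatment groups". No covariate or age subgroup is named. A further sentence plans Bonferroni-corrected comparisons of paired intervals, 0-3 and 0-6 months, without naming the variable.

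The baseline form (Appendix 1, Table 1) records birth date and both adenoid measures. After entry, the only stated use of age is the choice of radiographic measuring site in Appendix 3.

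**The concern.** The entry range crosses the age at which, on the protocol's account, normal adenoids stop growing and start to shrink. Over 12 months the youngest children may therefore drift one way and the oldest the other, whatever they are given. If so, pooling them without an age term adds scatter unrelated to treatment. In a trial of 34 per arm it also leaves the estimate open to a chance difference in age mix. Baseline size, another likely source of scatter, is recorded but unused. At stake is the trial's ability to answer the second question in its title. The primary RTI endpoint is not affected.

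**Working it through.** **1. The plan's own figure.** The SAP's sample size concerns RTIs: difference 2.0, SD 2.55, two-sided 0.05, 80% power. The normal approximation gives 2 × (1.960 + 0.842)² × (2.55/2.0)² = 25.5, so 26 per arm. The t-test gives 26.5, so 27 per arm, with power 80.7%. Allowing for 20% dropout, 27/0.8 = 33.75, so 34 per arm and 68 in all. The stated figures reproduce. No such calculation exists for adenoid size.

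**2. Assumptions needed for adenoid size** (none is in the documents).
- Effect: 2.0/2.55 = 0.78 residual SD, borrowed from the RTI calculation.
- Completers: 27 per arm.
- Share under 5 at entry, p: uniform ages give 3/4 = 75% if entry stops at the sixth birthday and 3/5 = 60% if it runs to the seventh.
- Natural 12-month change: +g for children under 5 and -g for the rest, in units of residual SD.

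**3. Loss of precision.** The two age groups differ by 2g in expected change, so the unadjusted variance is 1 + 4g²p(1-p). The standardised effect becomes 0.78 divided by the square root of that.

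| g | Variance, p = 0.75 | Variance, p = 0.60 | Power, p = 0.75 | Power, p = 0.60 |
|---|---|---|---|---|
| 0 | 1.00 | 1.00 | 80.7% | 80.7% |
| 0.25 | 1.05 | 1.06 | 78.9% | 78.4% |
| 0.5 | 1.19 | 1.24 | 73.7% | 71.9% |
| 1 | 1.75 | 1.96 | 57.1% | 52.4% |

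At g = 0.5, restoring the power without adjustment would need about 27 × 1.19 = 32 to 27 × 1.24 = 33.5 completers per arm.

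**4. Bias between arms.** In 20,000 simulated trials per setting, with no drug effect, 27 per arm and g of 0.5 or 1, the unadjusted test rejected in 4.9-5.3% of trials. The mean arm difference was within 0.005 SD of zero. There is no systematic bias.

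**5. Chance imbalance.** From exact binomials, the arms differ by 20 percentage points or more in the share aged 5 or over in 7-11% of trials with 34 per arm, and in 8-13% with 27. Such a gap shifts the estimate by 0.2 × 2g = 0.4g, which is 0.2 SD at g = 0.5. The residual standard error is √(2/34) = 0.24 or √(2/27) = 0.27 SD. This is the same noise as in step 3 seen in a single trial, not a second loss.

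**6. Within-arm change.** With no drug effect, the mean drift in one arm is pg - (1-p)g = (2p-1)g, that is 0.2g to 0.5g, and it is not zero. A paired test in one arm at 0.05/2 = 0.025 then rejects in 4-14% of trials at g = 0.5 and 7-36% at g = 1. Here g is taken as the change over the tested interval; over 3 or 6 months it would be smaller than over 12. With most children under 5 the net drift is towards growth, so a within-arm reading would tend to hide a benefit. In a mostly older group it would imitate one.

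**The case against.** The strongest reply is that randomisation with concurrent placebo already deals with natural change. Both arms have the same expected course, the type I error is kept, and a chance age imbalance is already reflected in the standard error and p value. This is right. A reader might infer from the turning point at 5 that the adenoid result is biased; for the planned between-arm comparison the documents do not support that.

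A reader might also infer that a drug which only slows growth in younger children could never meet an objective worded as reduction. That does not follow either, because slower growth still leaves smaller adenoids than placebo at 12 months.

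Second, the turning point describes normal children. The protocol's next sentence says that growth continues in some children with recurrent URTIs, the kind enrolled here. So the documents do not say that a 6-year-old in this trial is expected to shrink. Nor do they give an age course for the AC/SP ratio or choanal obstruction, which are not direct measures of tissue size. The opposing trends may be weak. At g = 0.25 the loss is about 2 points of power, and with no reversal at 5 the modelled loss could vanish.

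Third, the endpoint is secondary and carries no power claim.

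What survives is that age and baseline size are collected, may plausibly predict the outcome, and are left out of an analysis with few patients.

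**Conclusion.** The point holds as one of precision. Between arms the comparison is valid but may be less sensitive than the data allow. Under the stated assumptions, power of 81% falls to 78-79%, 72-74% or 52-57% as g goes from 0.25 to 0.5 to 1 residual SD. Which of these applies cannot be settled from the documents, because g, the SD and the effect for adenoid size are all missing and the 0.78 SD is borrowed from RTIs. If involution after 5 is weak in this population, the loss is at the small end or below it. Any gain from adjusting for baseline size comes on top and is not quantified here.

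Bias arises only if a change within an arm, for example in the paired 0-3 and 0-6 month comparisons, is read as a drug effect. The documents plan those comparisons but do not say that conclusions on the drug will rest on them. They should rule it out. The primary endpoint and its sample size stand.

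**What to change.** In the SAP, before unblinding:

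- Analyse the 12-month AC/SP ratio and percent choanal obstruction each by ANCOVA on arm, baseline value and age at entry.
- Enter age in years as a continuous variable and allow a change of slope near 5. Do not split at 5 on entry age: under uniform ages, 20-25% of the sample enters at age 4 (1/5 or 1/4) and passes 5 during follow-up.
- Judge normality on the model residuals. If they are clearly non-normal, use a rank-based or bootstrap version of the same model in place of Mann-Whitney U, which takes no covariate.
- State that the drug effect on adenoid size is the adjusted difference between arms, and that a fall from baseline within the OM-85 arm is descriptive only.

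The cost is two or three model terms and a changed non-normal fallback. With 54 completers, three added terms take the residual degrees of freedom from 52 to 49. No new data, visits or patients are needed, since birth date and both baseline measures are already on the baseline form.
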